Appendix 2.2. Endpoint Derivations

Height Growth

The primary efficacy endpoint is H defined by the following:

$$H_{ijkl} = \frac{Y_{ijkl} - Y_{i0kl}}{Z_{jl} - Z_{0l}},$$

where Y_{ijkl} is the observed standing height for the i th subject, at month j on dose k with gender factor l ($j=0$ denotes baseline measurement) and Z_{jl} is the mean expected standing height based on Merker for subject i 's age.

Mean expected standing height from Merker is sorted by 6 months up to age 4, while means expected values for children > 4 years are sorted per annum. Linear interpolation will be employed to calculate mean expected values so that mean standing height are sorted at 6 month intervals for children > 4 years. SAS code for the linear interpolation calculation will be provided in Appendix 4.

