## 1.2. Schema

### 1.3. Schedule of Activities

The SoA table provides an overview of the protocol visits and procedures. Refer to the [STUDY ASSESSMENTS AND PROCEDURES](#) section of the protocol for detailed information on each procedure and assessment required for compliance with the protocol.

The investigator may schedule visits (unplanned visits) in addition to those listed in the SoA table, in order to conduct evaluations or assessments required to protect the well-being of the participant.

	Enrollment	M1 b	M2 b	M3	M4 b	M5 b	M6	M7 b	M8 b	M9	M10 b	M11 b	M12	M13 b	M14 b	M15	M16 b	M17 b	M18	M19 b	M20 b	M21	M22 b	M23 b	M24	Early Term/Discon.	Follow-up	
Visit Identifier	1	2	3	4	5	6	7	8	9	10	11	12	13	14	15	16	17	18	19	20	21	22	23	24	25	26	27	
Days Relative to Day 1 a	1	29	61	91	121	151	181	211	241	271	301	331	361	391	421	451	481	511	541	571	601	631	661	691	721			
Visit Window (Days)	±7	±7	±7	±7	±7	±7	±7	±7	±7	±7	±7	±7	±7	±7	±7	±7	±7	±7	±7	±7	±7	±7	±7	±7	±7	±7	±7	
Informed consent/assent	X																											
Demography c	X																											
Medical history	X																											
Pregnancy test c	X	X	X	X	X	X	X	X	X	X	X	X	X	X	X	X	X	X	X	X	X	X	X	X	X	X	X	
Contraception check c	X	X	X	X	X	X	X	X	X	X	X	X	X	X	X	X	X	X	X	X	X	X	X	X	X	X	X	
Inclusion/Exclusion Check	X																											
Randomisation	X																											
Physical examination d				X			X			X			X			X			X			X			X	X		
Neurological examination				X			X			X			X			X			X			X			X	X		
Weight				X			X			X			X			X			X			X			X	X		
Vital signs				X			X			X			X			X			X			X			X	X		
Hematology				X			X			X			X			X			X			X			X	X		
Blood chemistry				X			X			X			X			X			X			X			X	X		
Study intervention dispensing	X	X	X	X	X	X	X	X	X	X	X	X	X	X	X	X	X	X	X	X	X	X	X	X	X	X		
Study intervention administration	X	→	→	→	→	→	→	→	→	→	→	→	→	→	→	→	→	→	→	→	→	→	→	→	→			
Dosing diary	X	→	→	→	→	→	→	→	→	→	→	→	→	→	→	→	→	→	→	→	→	→	→	→	→			
Anthropometry				X			X			X			X			X			X			X			X	X		

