## **8.1. Efficacy Assessments**

### **8.1.1. Anthropometric Measurements**

Anthropometric measurements for height and proportionality will be performed and reported in the eCRF. Anthropometric measurements will be performed according to a trial-specific Anthropometric Measurement Manual, which will be provided to the investigational sites. This manual will contain a detailed description on the following:

- Which measurements to perform.
- The tools/instruments to be used.
- Standard procedure for performing these measurements.

The measurements to be taken on a 3-monthly basis are:

- Standing height (length for participants <2 years of age);
- Sitting height (crown-rump length for participants <2 years of age);
- Knee height;
- Head circumference;
- Arm span;
- Body weight;
- Elbow extension angle;
- Cranial dimensions (occipito-frontal, occipito-nasal distances).

Waist and chest circumference will be measured at baseline and at final visit.

Anthropometric data will only be collected by appropriately trained individuals at the trial site and in accordance with the anthropometric measurement manual. All sites will follow a consistent, structured and documented training program. This will occur prior to trial start, through regular refresher training and at targeted retraining based on analysis of measurement data consistency at the site.

Sites will be required to make all efforts to have the same anthropometrist at each visit for each participant (longitudinal consistency) and between participants (cross-sectional consistency). As well as following the specific procedures for measurement laid out in the measurement manual, sites will be provided with the same (or exactly equivalent) equipment across all sites and will follow the specific calibration procedures.

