4.2.1. Analyses for Longitudinal Continuous Endpoints

Mixed-effect, repeated measures (MMRM) models will be used. The fixed effects of treatment, visit, treatment-by-visit interaction, age and gender will be included. Visit will be modeled as a categorical covariate. (If the model does not converge then Visit will be modeled as a continuous covariate.) Unstructured covariance matrix will be assumed for the model errors. Compound symmetry covariance matrix will be used if the model with unstructured variance covariance doesn't converge.

When modeling the change from baseline values, the variable for visit will start with the first post-baseline visit. At each visit, estimates of least square mean (LSM) values and the LSM differences between treatment groups will be derived from the model. The corresponding p-values and 95% confidence intervals will also be derived from the model.

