5. ANALYSES AND SUMMARIES

5.1. Primary Endpoint(s)

5.1.1. Increase in height growth above expected in reference population

5.1.1.1. Main Analysis

- Estimand strategy: Hypothetical ([Section 1.1.1](#)).
- Analysis set: FAS ([Section 3](#)).
- Analysis methodology: Change from baseline relative to Merker (2018) will be analyzed using MMRM including data from Months 3-24 with gender (and possibly age), and whether a subject has switched doses of recifercept as covariates, subject (and/or time) as a random effect and an unstructured covariance matrix ([Section 4.2.1](#)).
- Intercurrent events and missing data: Data after study drug discontinuation and rescue will be excluded; intermediate missing values will not be imputed.
- The sample size, mean, standard deviation, median, minimum, and maximum at the baseline and postbaseline visits for observed standing height and change from baseline will be presented for each treatment arm.
- The least-squares (LS) means, the 95% confidence interval for the LS means, the difference between the LS means for each pair of treatment groups, and the corresponding 95% confidence interval will be presented for change from baseline in standing height for all postbaseline visits.

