Appendix 2.3. Definition of Protocol Deviations That Relate to Statistical Analyses/Populations

Appendix 3. Data Set Descriptions

Appendix 4. Statistical Methodology Details

Linear Interpolation

Linear interpolation will be employed to provide mean expected standing height values at 6 month interval for children > age 4. The SAS code is as follows:

```
proc expand data=mydata out=LinInterp;  
    convert exp_mean=linear / method=join;  
    id age;  
run;
```

MMRM

MMRM will be used for height growth and arm span-height difference. The SAS code is as follows:

```
proc mixed data=mydata;  
    class dose gender month;  
    model height = dose month gender age/s;  
    random int month / type=un sub=subject;  
    lsmean dose;  
run;
```

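### The reference height is specified only at 6-month ages, but the primary growth ratio is needed at 3-monthly visits and at each child's own age

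*SAP*

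**What the plan says.** SAP Appendix 2.2 defines H = (Y_j − Y_0)/(Z_j − Z_0). Y is observed standing height and Z is the mean reference height for the subject's sex and age. The reference table "is sorted by 6 months up to age 4" and is annual above that. The interpolation step is described as producing values so that "mean standing height are sorted at 6 month intervals for children > 4 years". SAP Appendix 4 repeats the target: "Linear interpolation will be employed to provide mean expected standing height values at 6 month interval for children > age 4". Its code joins the reference points linearly by age, but names no visit ages and no output spacing.

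Protocol 8.1.1 introduces the height measurements with "The measurements to be taken on a 3-monthly basis are", and the Schedule of Activities marks anthropometry at Months 3, 6, 9 and so on to Month 24. SAP 5.1.1.1 analyses growth relative to the reference with an "MMRM including data from Months 3-24". SAP 4.2.1 adds that "Visit will be modeled as a categorical covariate" and "At each visit, estimates of least square mean (LSM) values" will be derived.

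Neither document says how Z is obtained when a child's age at a measurement falls between grid points.

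**The concern.** The stated grid is coarser than the visit schedule. Even for a child whose baseline age falls exactly on a 6-month point, four of the eight modelled visits (Months 3, 9, 15 and 21) fall between points. For any other child, the baseline and nearly all visits do. The planned interpolation does not close this gap: it covers only ages above 4 and stops at 6-month spacing.

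The trial has no concurrent control, so the denominator carries the comparison with untreated growth. Two programmers could follow the same text and produce different primary data, one by looking values up and the other by interpolating to exact age. Under look-up, a Month 3 denominator can be zero, so H would be missing because of a birth date, which the SAP's missing-data rules do not address. At Months 9, 15 and 21 the errors would look like ordinary growth ratios.

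**Working it through.** The plan gives no figure for this point to reproduce. The check asks what H becomes for a child growing exactly as the reference (true H = 1) if Z is read from the 6-month grid.

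**Inputs from the documents.** Target days 91, 271, 451, 631 and 721 for Months 3, 9, 15, 21 and 24 (Schedule of Activities; SAP Appendix 2.1). Grid step of 6 months (SAP Appendices 2.2 and 4).

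**Assumptions.** Z is taken from the nearest or the previous grid point (both give the same result). Growth velocity is constant, so it cancels from the ratio. There is no drug effect. Baseline ages are spread evenly between grid points. Elapsed time starts at Day 1; this is relaxed below.

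**Formula.** Elapsed months m = (Day − 1)/30.4375; k = the whole number of 6-month steps in m; p = (m − 6k)/6. The denominator spans k + 1 steps with probability p and k steps with probability 1 − p. Then H = m/(6 × steps), and for k ≥ 1 its SD is the difference between the two values × √[p(1 − p)].

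Month 9, for example: m = 270/30.4375 = 8.871, k = 1, p = 2.871/6 = 0.478. H is 8.871/6 = 1.478 with probability 0.522, or 8.871/12 = 0.739 with probability 0.478. The mean is 1.12 and the SD is 0.739 × √(0.478 × 0.522) = 0.37.

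| Visit | m | H (share of children) | Mean | Added SD |
|---|---|---|---|---|
| Month 3 | 2.957 | undefined (51%) or 0.49 (49%) | – | – |
| Month 9 | 8.871 | 1.48 (52%) or 0.74 (48%) | 1.12 | 0.37 |
| Month 15 | 14.784 | 1.23 (54%) or 0.82 (46%) | 1.04 | 0.20 |
| Month 21 | 20.698 | 1.15 (55%) or 0.86 (45%) | 1.02 | 0.14 |

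Random visit timing within ±7 days leaves the means and SDs at Months 9, 15 and 21 essentially unchanged.

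**Month 24 and the baseline date.** The Schedule of Activities marks no anthropometry at Enrollment, and SAP 1.1.1 refers to a baseline from C4181005. The baseline height may therefore precede Day 1 by a gap that the documents do not state. Day 721 is 720 days after Day 1, and four grid steps are 4 × 182.625 = 730.5 days. With no gap the added SD at Month 24 is 0.08. With a gap of 10.5 days it is 0.00, because 720 + 10.5 = 730.5. With a gap of 30 days it is about 0.06. The mean is 1.00 in each case.

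The same 30-day gap does not remove the intermediate-visit problem. At Month 9, elapsed time is 300 days, so H is 300/182.625 = 1.64 or 300/365.25 = 0.82. The added SDs at Months 9, 15 and 21 become 0.39, 0.21 and 0.15.

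**Visit-averaged means.** With no gap, the null means at Months 3, 6, …, 24 are 0.493, 0.986, 1.125, 1.014, 1.042, 1.007, 1.021 and 1.004 (defined ratios only at Months 3 and 6). Their simple average is 7.692/8 = 0.96 rather than 1. This is illustrative, since the model's weighting would differ. It is relevant because the Appendix 4 code requests dose means with no dose-by-month term.

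**Check of the remedy.** With Z interpolated to exact age, the denominator under constant velocity is velocity × elapsed time, so H = 1 at every visit. Under an assumed decelerating reference (4 + 6·exp(−(age − 1)/1.2) cm/year, points every 6 months to age 4 and yearly after), the mean is 0.999 at every visit with SD at most 0.011.

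**The case against.** The strongest reply is that the look-up is an assumed reading. Appendix 2.2 defines Z for the subject's age, and the Appendix 4 code joins points linearly with age as the index. A programmer could take that to exact age and get a correct denominator. This stands. A reader might infer that the plan cannot yield a correct H; the documents do not support that. They describe a 6-month target, which would serve little purpose if exact-age values were intended, but they do not prescribe look-up.

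Second, the estimand is at Month 24 and SAP 4.1 states no hypotheses. This also stands: the Month 24 mean is essentially untouched, and under no drug effect the look-up error does not depend on dose.

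Third, the last bullet of SAP 5.1.1.1 reports means by visit for change in standing height, which has no reference denominator, and the Appendix 4 model statement also names height. The text is therefore mixed on whether visit-level means of H will be reported at all. The same section does put growth relative to the reference into the model, so the intermediate values of H still enter the fit.

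Fourth, zero denominators at Month 3 would show up when the code is first run, and the repair might then extend to the other visits. That is plausible, but a local repair at Month 3 would leave believable wrong values at Months 9, 15 and 21.

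**Conclusion.** The point holds as a mismatch between a 6-month reference grid and a 3-monthly, own-age endpoint, with no rule for the ages between. The mismatch needs no assumption. Its size does: under look-up, constant velocity, no drug effect and evenly spread baseline ages, added SDs of H are about 0.37, 0.20 and 0.14 at Months 9, 15 and 21, and about half of Month 3 ratios are undefined. The harm is to the intermediate visits that feed the mixed model and to any by-visit or visit-averaged means of H.

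A reader might infer that the Month 24 result is biased or materially less precise. The documents do not support that. The mean stays at about 1.00, and the added SD ranges from 0.00 to 0.08 for baseline gaps of 0 to 30 days, a gap the documents do not give. A reader might also infer that Y_0 and Z_0 are taken at different dates. No text says so, and the shared index for baseline points the other way. This is a cheap improvement, not a threat to the Month 24 mean.

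**What to change.** In SAP Appendices 2.2 and 4, state that the sex-specific reference height is linearly interpolated at all ages, including under 4, to the child's age on the actual date of each height measurement, including the baseline height used as Y_0. Where only month and year of birth are recorded (the minimum that Protocol 8 requires), fix one day-of-birth convention and use it for both Z_j and Z_0. Replace the 6-month target in both appendices, and supply code that outputs Z at those ages.

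The cost is a few lines of SAP text and code. The linear joining method already in Appendix 4 can be reused. At least month and year of birth and the dates of measurement are available, so no new data and no protocol change are needed.

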Appendix 2.3. Definition of Protocol Deviations That Relate to Statistical Analyses/Populations

Appendix 3. Data Set Descriptions

Appendix 4. Statistical Methodology Details

Linear Interpolation

Linear interpolation will be employed to provide mean expected standing height values at 6 month interval for children > age 4. The SAS code is as follows:

```
proc expand data=mydata out=LinInterp;  
    convert exp_mean=linear / method=join;  
    id age;  
run;
```

MMRM

MMRM will be used for height growth and arm span-height difference. The SAS code is as follows:

```
proc mixed data=mydata;  
    class dose gender month;  
    model height = dose month gender age/s;  
    random int month / type=un sub=subject;  
    lsmean dose;  
run;
```

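### The SAP's printed MMRM code and Appendix 1 omit the dose-by-visit term, and the code requests only visit-averaged dose means, so it does not return the Month 24 result that the primary estimand needs

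*SAP*

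**What the plan says.** **Model in the body of the SAP.** Section 4.2.1 states: "The fixed effects of treatment, visit, treatment-by-visit interaction, age and gender will be included". Visit is categorical.

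**Outputs in the body.** Section 4.2.1 continues: "At each visit, estimates of least square mean (LSM) values and the LSM differences between treatment groups will be derived from the model", and then "The corresponding p-values and 95% confidence intervals will also be derived from the model". Section 5.1.1.1, the main analysis of height growth, refers to 4.2.1 and promises LS means, pairwise dose differences and 95% intervals for every postbaseline visit. Section 5.2.1.1 does the same for the arm span-height difference.

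**Estimand.** Section 1.1.1 sets the population summary as the mean height growth at 24 months, adjusted for age and gender. Appendix 2.2 defines height growth as H, the observed change in height divided by the change expected from the reference population.

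**Model in the appendices.** Appendix 1 lists time, dose, gender and age for the main and per-protocol analyses of both endpoints, with no interaction. Appendix 4 says "MMRM will be used for height growth and arm span-height difference" and prints "model height = dose month gender age/s", then "random int month / type=un sub=subject", then `lsmean dose`.

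**Convergence.** Section 4.2.1 gives two fallbacks: "If the model does not converge then Visit will be modeled as a continuous covariate", and "Compound symmetry covariance matrix will be used if the model with unstructured variance covariance doesn't converge". It does not say which comes first.

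**The concern.** The body and the appendices describe different models and different outputs for the primary efficacy endpoint. A programmer who follows 4.2.1 obtains an estimate for each dose at each visit, including Month 24. A programmer who copies Appendix 4 obtains one average per dose over the whole follow-up, with no interval. Only the first matches section 1.1.1. No hypothesis test depends on this, since SAP 4.1 states that there are none. What is at stake is which number is reported as the primary efficacy estimate, and whether it carries a confidence interval.

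Smaller inconsistencies in the same text add to the uncertainty:

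- The output bullets of 5.1.1.1 and 5.2.1.1 are labelled as standing height, although the analysed variables are H and the arm span-height difference.
- The arm span row of Appendix 1 says Month 12, where SAP 1.1.2 and protocol 9.3.3 say 24 months.
- Age is optional in 5.1.1.1 and missing from the covariate list in 5.2.1.1, although 1.1.1, 1.1.2 and 4.2.1 require it.
- The dose-switch covariate of 5.1.1.1 and 5.2.1.1 is not in the code.
- Protocol 9.3.2 still describes an ANOVA on dose.

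**Working it through.** The documents give no figure to reproduce here. The check compares what is promised with what the printed statements return.

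**Inputs**

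- 3 doses (SAP 1.2).
- 8 postbaseline height visits, Months 3, 6, 9, 12, 15, 18, 21 and 24 (three-monthly anthropometry in protocol 8.1.1; Months 3 to 24 in SAP 5.1.1.1).

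**Promised outputs**

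- LS means: 3 doses × 8 visits = 24, each with a 95% interval.
- Within-visit dose differences: 3 pairs × 8 visits = 24, each with a 95% interval.

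**Outputs of the printed code**

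- `lsmean dose` returns 3 means, one per dose, with the months weighted equally. It requests neither confidence limits nor differences.
- The `/s` option in "model height = dose month gender age/s" prints two dose-versus-reference coefficients with standard errors. Without an interaction, each is a single difference common to all 8 visits.
- The dose-and-visit part of the design has rank 1 + 2 + 7 = 10 as printed. With the interaction it has rank 3 × 8 = 24, one free mean per dose and visit.

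**Both statements matter.** If the interaction is added and `lsmean dose` is left alone, the output is still averaged over months. If only the LS-means request is changed, a Month 24 mean can be obtained, but the dose differences stay equal at every visit.

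**Size of the error in level**

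- Centre of the averaged visits: (3 + 6 + 9 + 12 + 15 + 18 + 21 + 24)/8 = 108/8 = 13.5 months.
- For a linear drift in H over Months 3 to 24, alike in all doses, the share missed at Month 24 is (24 − 13.5)/(24 − 3) = 10.5/21 = 0.5.
- With no drift the error is zero. H is a ratio of cumulative growth to expected cumulative growth, so zero drift is possible.

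**Dose differences.** A difference that is constant over visits is recovered in full. For one that changes over time, the common coefficient is a weighted average over visits, and the weights depend on the within-child covariance of H. The documents give no information on that covariance, so no figure is offered.

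**Covariance statement.** With month in CLASS, "random int month / type=un sub=subject" has 1 + 8 = 9 random effects, hence 9 × 10/2 = 45 parameters, plus 1 residual variance = 46. An 8 × 8 covariance matrix has 8 × 9/2 = 36 distinct elements, so at most 36 parameters can be identified. The code is following the body here: 5.1.1.1 and 5.2.1.1 ask for a random effect of subject, time or both together with an unstructured covariance.

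**The case against.** The strongest reply is that 4.2.1 governs and Appendix 4 is a sketch. Sections 5.1.1.1 and 5.2.1.1 cite 4.2.1 and do not cite Appendix 4. The code uses a placeholder data set and one response name for two endpoints, so it cannot be run unedited for the arm span-height difference. Protocol 9.3 requires the SAP to be final before any analysis.

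Much of this stands: the body, read alone, does imply a Month 24 LS mean of H. But Appendix 4 is presented as the code for these analyses, Appendix 1 repeats the omission in every MMRM row, and no sentence ranks the appendices below the body. A final SAP that contains both models still leaves the choice open.

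A reader might infer several stronger things that the documents do not support:

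- *The missing interaction alone prevents a Month 24 mean.* It does not. An added ESTIMATE statement could obtain one from the additive fit, with equal dose differences imposed. The LS-means request is also at fault.
- *The code yields no dose contrasts.* It yields two, through `/s`, but they are not specific to any visit.
- *Dose differences are biased by a known fraction.* That fraction depends on an assumed covariance, and a constant difference is not biased at all.
- *The excess covariance parameters bias the result.* They create a risk of non-convergence, not bias in themselves.
- *Omitting or including the switch covariate shifts the LS means by a calculable amount.* That depends on how the covariate is coded, which neither document states.

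**Conclusion.** The point holds as an internal inconsistency in the SAP that should be corrected before analysis. As printed, Appendix 4 supplies 3 visit-averaged means without intervals in place of 24 by-visit means and 24 within-visit differences with intervals, and none of the 3 is the Month 24 mean of section 1.1.1. The counts need no assumption beyond the 3 doses, the 8 visits and the standard behaviour of the printed statements. The error in level at Month 24 is half of any common linear drift in H over Months 3 to 24, and zero if there is none; how far H will drift is unknown. The effect on dose differences is left unquantified. The finding concerns which estimate is reported, not the validity of a test.

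**What to change.** **Appendix 4.** Replace the MMRM code with:

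`class subject dose gender month;`
`model H = dose month dose*month gender age / s;`
`repeated month / type=un subject=subject;`
`lsmeans dose*month / cl diff;`

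The DIFF option prints 24 × 23/2 = 276 pairs; report only the 24 within-visit dose pairs. Run the same code separately with change in arm span-height difference as the response.

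**Appendix 1.** Add the dose-by-month term to the MMRM rows, relabel the height row as H, and change the arm span row from Month 12 to Month 24.

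**Sections 5.1.1.1 and 5.2.1.1.**

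- Replace the random-effect wording with an unstructured within-subject covariance; otherwise the new REPEATED statement would contradict the text.
- Make age a fixed covariate in both.
- Correct the output labels to H and to arm span-height difference.
- State that the Month 24 LS mean of H per dose, with its 95% interval, is the primary efficacy result.

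**Section 4.2.1.** Order the fallbacks: simplify the covariance first and keep visit categorical, so that the Month 24 mean does not come to rest on an assumed straight line.

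**Dose switching.** Reconcile the covariate between the text and the code. Switching happens after baseline, so a supplementary analysis is the better place for it, but that is a separate point.

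**Protocol 9.3.2.** Align the ANOVA description with the SAP at the next amendment.

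The cost is SAP code and wording plus that short protocol alignment. No new data are required.

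### The SAP gives three inconsistent covariance models for the primary MMRM, and its compound-symmetry fallback does not fit the growth ratio H

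*SAP*

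**What the plan says.** SAP 4.2.1, the general method: "Unstructured covariance matrix will be assumed for the model errors". No random effect is mentioned there.

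SAP 5.1.1.1, the primary analysis, specifies an "MMRM including data from Months 3-24" and adds "subject (and/or time) as a random effect and an unstructured covariance matrix", citing 4.2.1. SAP 5.2.1.1 repeats this for the arm span-height difference.

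SAP Appendix 4, the code meant for both endpoints, declares "class dose gender month" and then "random int month / type=un sub=subject". It has no REPEATED statement, so a separate residual variance is added. The response is height, there is no dose-by-month term, and least-squares means are requested by dose only.

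SAP 4.2.1 gives two fallbacks, both triggered by non-convergence: "If the model does not converge then Visit will be modeled as a continuous covariate" and "Compound symmetry covariance matrix will be used if the model with unstructured variance covariance" structure fails to converge. It does not say which is tried first, or what happens if a fit converges with a singular random-effects matrix.

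SAP Appendix 2.2 defines the endpoint as H = (Y_j − Y_0)/(Z_j − Z_0): observed height change over the change expected from the reference population.

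**The concern.** Two of the three specifications have more covariance parameters than the data can separate. Over-parameterised mixed models may fail to converge or may return a singular matrix. The analyst would then either apply a fallback or choose a structure after seeing the data.

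The fallbacks matter because of how H is built. Its denominator grows with every visit, so a given height measurement error counts for much more at Month 3 than at Month 24. Compound symmetry assumes the same variance at every visit. It would therefore overstate uncertainty at Month 24 and understate it early on, and 5.1.1.1 reports 95% intervals at all post-baseline visits. A linear visit term changes the mean model as well, and can move the Month 24 estimate itself.

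**Working it through.** The documents give no interval width, variance or power figure to reproduce. The check has four parts.

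**1. Parameter counts.** Protocol 8.1.1 ("The measurements to be taken on a 3-monthly basis are" listed there, height included) and Months 3-24 give 8 visits. An 8×8 covariance matrix has 8×9/2 = 36 distinct elements.

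| Source | Covariance parameters | Rank |
|---|---|---|
| SAP 4.2.1: unstructured errors | 36 | 36 |
| SAP 5.1.1.1 and 5.2.1.1: subject effect plus unstructured errors | 36 + 1 = 37 | 36 |
| Appendix 4: intercept plus 8 class months, unstructured, plus residual | 9×10/2 + 1 = 46 | 36 |
| Appendix 4 with month continuous | 2×3/2 + 1 = 4 | 4 |

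The rank is that of the linear map from the parameters to the 8×8 marginal covariance. In the Appendix 4 model 10 parameters are redundant, but the marginal matrix is still fully unstructured.

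**2. Variance of H by visit.** Assumed inputs, none of them in the documents: expected growth v = 5 cm/year, height measurement SD s = 0.5 cm (range 0.3-0.7), between-child SD of the true ratio b = 0.2, 21 children per dose (63/3; the split is not given), complete data, baseline at Day 1.

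Var(H_j) = b² + 2s²/(v·t_j)², with t_j = 0.25j years, j = 1 to 8.

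- Month 3: 0.04 + 0.5/1.25² = 0.36, SD 0.60.
- Month 24: 0.04 + 0.5/10² = 0.045, SD 0.21.
- Mean over the 8 visits: 0.04 + (0.5/1.25²)·(Σ1/j²)/8 = 0.04 + 0.32 × 0.1909 = 0.1011.

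**3. Compound symmetry with categorical visit.** With complete data the fitted common variance is the mean of the visit variances.

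- Month 24 SE ratio: √(0.1011/0.045) = 1.50. The 95% half-width is 1.96·√(0.1011/21) = 0.136 instead of 1.96·√(0.045/21) = 0.091.
- Month 3 SE ratio: √(0.1011/0.36) = 0.53.
- For s = 0.3 to 0.7 the Month 24 ratio runs from 1.22 to 1.79.
- A simulation of 2,000 trials at s = 0.5 gave a compound-symmetry SE of 0.069 at Month 24 against an empirical 0.046.

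A wider set of assumptions (v 4-5 cm/year, between-child velocity SD 0.6-1.0 cm/year, s 0.3-0.5 cm, within-child quarterly increment SD 0-0.3 cm) gives Month 24 ratios of 1.22 to 1.97. The upper end comes, for example, from v = 5, b = 0.6/5 = 0.12, s = 0.5: √((0.0144 + 0.0611)/(0.0144 + 0.005)) = √(0.0755/0.0194) = 1.97. In 4,000 simulated trials for each of two Day 1 cases, Month 24 coverage was 99.1% and 100% under compound symmetry, and 94.9% in both under an unstructured matrix.

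If baseline is taken 12 months earlier (an assumption; the documents do not give the parent study's length), t_j becomes 1 + 0.25j. With v = 5, s = 0.5 and b = 0.2 the mean variance is 0.0457 and the Month 24 variance is 0.04 + 0.5/15² = 0.0422, so the ratio is √(0.0457/0.0422) = 1.04. Over the wider set it is 1.02 to 1.13.

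**4. Continuous visit.** If the ratio is constant or linear in time there is no bias. Suppose instead that it rises evenly from 1.0 to 1.5 by Month 12 and then stays flat. The visit means are 1.125, 1.25, 1.375 and then 1.5 five times, with average 1.406. Under compound symmetry the fit is an ordinary straight line: slope 2.125/42 = 0.0506 per visit, so the Month 24 estimate is 1.406 + 3.5 × 0.0506 = 1.58 against a true 1.50. An unstructured matrix, which gives later visits more weight, gave 1.52 in one assumed variance case.

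**The case against.** A reader might infer that the primary model cannot be estimated, or that its intervals are invalid as planned. The documents do not support that. Section 4.2.1 alone is a standard identified model, and 5.1.1.1 refers to it. In the redundant versions only the split between random effects and residual is unidentified; the marginal covariance, the least-squares means and their intervals remain estimable.

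Nor can one say that a fallback is likely, or that linear visit comes before compound symmetry. No fit of the 46-parameter model has been run, the triggers refer only to non-convergence, and the order is not given. It would also be wrong to say that continuous visit always leaves the redundancy in place. If month leaves the class statement in the Appendix 4 code, the result is a random intercept and slope with 4 identified parameters, and the Month 24 standard error is then correct in complete data. The redundancy persists only under the literal 5.1.1.1 wording.

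The size depends on the baseline. SAP 1.1.1 attributes it to study C4181005, which could mean that study's own baseline, and the excess is then small. Against that, Protocol 1.3 schedules no anthropometry at enrolment, and SAP 2.4 takes the latest available value, from C4181005 where Day 1 is missing. A baseline near Day 1 is the better-supported reading, although a last visit some time before Day 1 would reduce the effect somewhat.

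Finally, the Month 24 error is conservative, and SAP 4.1 states that there are no hypotheses. That stands, and it lowers the severity. It does not cover the early visits, where intervals would be too narrow, or the p-values for dose differences in 4.2.1.

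**Conclusion.** The point holds as an inconsistency with a poorly chosen fallback. It should be fixed before analysis, but it does not invalidate the primary analysis. The parameter counts follow directly from the text. That the variance of H falls over visits follows from its formula with ordinary measurement error.

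The size is conditional. With a baseline near Day 1 and the assumed variances, compound symmetry makes the Month 24 interval about 22% to 97% too wide, and in the base case it puts the Month 3 standard error at about half its true value. With a baseline 12 months earlier the Month 24 excess is about 2% to 13%. Continuous visit misplaces the Month 24 estimate only when the ratio is not linear in time. These figures apply to H. They do not carry over to a change in centimetres, such as the arm span-height difference, for which only the inconsistency of specification is shown here.

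**What to change.** - Use one specification in SAP 4.2.1, 5.1.1.1, 5.2.1.1 and Appendix 4: `repeated month / type=un subject=subject`, with no RANDOM statement and visit always categorical.
- Replace the homogeneous compound-symmetry and continuous-visit fallbacks with an ordered list that keeps visit-specific variances, for example heterogeneous Toeplitz, then heterogeneous compound symmetry. State the trigger for each step.
- In the Appendix 4 code, set the response to H for the primary endpoint and to the change in arm span-height difference for the secondary. Add dose-by-month, and request dose-by-month least-squares means with 95% intervals. Without these changes, correcting the covariance line still produces no Month 24 interval for the ratio.

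The cost is SAP wording and a few lines of code, with no new data.
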